 - 8. percentage of the tissue affected on the slide image(s) (0 for none, 1 for >0 and <33%, 2 for 33-66%, and 3 for >66%); blinded readers will assess the percentage of tissue involved, considering both biopsies for a given segment (note that in the original GHAS, this component was measured as "number of biopsies affected")
- For items 1-7, the single highest scoring feature from each of the biopsies will be used as the score for that feature.
- The sum of the scores from the 8 histologic features within a region (terminal ileum, right colon, transverse colon, left colon, rectum) will be used as the Total score for that region (range 0-16). Furthermore,

CONFIDENTIAL – FOIA Exemptions Apply in U.S.

Total Ileum:

- The Ileal score will be equal to the Total Ileum Score.
- If any of the items 1-8 is missing, the Total Ileal score is missing. However, if items 1, 4, 5, and 6 are non-missing, then histologic ileal remission (defined in the Table below) can still be determined.

Total Colonic score:

- The worst available scores for each feature across the right colon, transverse colon, left colon, and rectum will be summed to obtain a Total Colonic score.
- If the worst score across the right colon, transverse colon, left colon, and rectum for any of the items 1-8 is missing, then the Total Colonic score is missing. However, if items 1, 4, 5, and 6 are non-missing, then histologic colonic remission (defined in the Table below) can still be determined.

Total Subject score:

- The worst available scores for each feature across the 5 regions will be summed to obtain a Subject Score
- If the worst score across the ileum, right colon, transverse colon, left colon, and rectum for any of the items 1-8 is missing, then the Total Subject score is missing. However,
 - If items 1, 4, 5, or 6 corresponding to the subject are non-missing, then histologic remission can be determined.
 - If items 1, 4, 5, and 6 corresponding to the subject are all non-missing and all equal to 0 (Q1=Q4=Q5=Q6=0), then the participant is considered to be in histologic response even in the presence of missing scores for items 2, 3, 7, and 8; otherwise, histologic response cannot be determined if at least one of items 2, 3, 7 or 8 is missing.

If both biopsies within a region (ileum, right colon, transverse colon, left colon and rectum) are missing or unevaluable, the GHAS score will be missing for that region.

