The definitions of baseline disease activity and histologic remission using the GHAS System apply to a segment (region), Ileal, Colonic, and Subject level; the range of possible scores is 0 - 16 irrespective of extent of the area being analyzed. The binary (yes or no) endpoints histologic response, histo-endoscopic response, and histo-endoscopic remission will be evaluated on a subject level only.

Term	Scope	Definition
Baseline Active Disease (GHAS)	Subject-level	GHAS with a score > 0 for infiltration of
	Ileal Colonic	polymorphonuclear cells in the lamina propria, polymorphonuclear cells in epithelium, or presence of erosions and/or ulcers $[Q1 > 0 \text{ or } Q4 > 0 \text{ or } Q5 > 0 \text{ or } Q6 > 0]$
Histologic Response (GHAS)	Subject-level	\geq 50% reduction in subject-level GHAS score from baseline, or absence of mucosal neutrophils (epithelium and lamina propria), epithelial damage, erosions and ulceration [Q1 = 0, Q4 = 0, Q5 = 0 and Q6 = 0]

Histologic Remission (GHAS)	Subject-level Ileal Colonic	Absence of mucosal neutrophils (epithelium and lamina propria), epithelial damage, erosions and ulceration [Q1 = 0, Q4 = 0, Q5 = 0 and Q6 = 0]
Histo-Endoscopic Response (GHAS)	Subject-level	Combination of histologic response and endoscopic response (≥50% improvement from baseline in SES-CD score)
Histo-Endoscopic Remission (GHAS)	Subject-level	Combination of histologic remission and endoscopic remission (SES-CD \leq 4 and at least a 2-point reduction from baseline and no subscore greater than 1 in any individual component)
Histo-Endoscopic Remission (GHAS, Alternative Definition)	Subject-level	Combination of histologic remission and endoscopic remission (SES-CD Score <2).

Geboes Grading System

Histological disease activity will be scored in a blinded manner by an experienced pathologist using the Geboes Scoring system (GS). The GS is a 7-item scale (with 4 levels of severity for each item) that categorizes inflammation as grade 0 (architectural change only), grade 1 (chronic inflammation), grade 2 (2a, lamina propria eosinophils and 2b, lamina propria neutrophils), grade 3 (neutrophils in the epithelium), grade 4 (crypt destruction), or grade 5 (erosion or ulceration), as illustrated in Table 5.

Grade 0	Structural (architectural change)
Subgrades	
0.0	No abnormality
0.1	Mild abnormality
0.2	Mild or moderate diffuse or multifocal abnormalities
0.3	Severe diffuse or multifocal abnormalities
Grade 1	Chronic inflammatory infiltrate
Subgrades	

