1.0	No increase
1.1	Mild but unequivocal increase
1.2	Moderate increase
1.3	Marked increase
Grade 2	Lamina propria neutrophils and eosinophils
2A Eosinophils	
2A.0	No increase
2A.1	Mild but unequivocal increase
2A.2	Moderate increase
2A.3	Marked increase
2B Neutrophils	
2B.0	None
2B.1	Mild but unequivocal increase
2B.2	Moderate increase
2B.3	Marked increase
Grade 3	Neutrophils in epithelium
3.0	None
3.1	< 5% crypts involved
3.2	< 50% crypts involved
3.3	> 50% crypts involved
Grade 4	Crypt destruction
4.0	None
4.1	Probable-local excess of neutrophils in part of crypt
4.2	Probable-marked attenuation
4.3	Unequivocal crypt destruction
Grade 5	Erosion or ulceration
5.0	No erosion, ulceration, or granulation tissue
5.1	Recovering enithelium+adjacent inflammation
5.2	Probable crosion—focally stripped
5.3	Unequivocal erosion
5.4	Ulcer or granulation tissue

Table 5:Grading Criteria for the histological evaluation of Disease Activity in CD
(Geboes grading system)

- At each time point, all biopsies (up to 2 biopsies per region) obtained from each of the predefined anatomic regions will be scored separately for each of the 7 items:
- The single highest scoring item from each of the biopsy will be used as the score for that item.
- The Ileal score is equal to the highest grade with a score > 0 (eg, a score of 3 for Grade 5 will be a 5.3 regardless of the scores for the other grades). All items within the ileum must be non-missing to obtain an Ileal score.
- The Colonic score is equal to the highest grade with a score > 0 across the right colon, transverse colon, left colon, and rectum.
- The Subject score is equal to the highest grade with a score > 0 across the ileum, right colon, transverse colon, left colon, and rectum.

If both biopsies within a region are missing or unevaluable, the GS will be missing for that region. The definitions of baseline disease activity and histologic remission using the Geboes Scoring

System apply to a segment (region), Ileal, Colon, and Subject level. Histologic response, histoendoscopic response, and histo-endoscopic remission will be evaluated on a subject level only.

Term	Scope	Definition
Active Disease (GS)	Subject-level	>2B.0 [Grade 2B \neq 0 OR Grade 3 \neq 0 OR Grade 4 \neq 0 OR
	Ileal	Grade $5 \neq 0$]
	Colonic	
Histologic Response (GS)	Subject-level	\leq 3.1, indicating neutrophil infiltration in <5% of crypts, no crypt destruction and no erosions, ulcerations or granulation tissue)

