5.5.2.10. Histologic assessments

Histologic endpoints - GHAS

- Change from baseline in the Ileal GHAS score at Week 12, Week 48, and Week 96 (among participants with Ileal histologic disease at baseline per GHAS)
- Change from baseline in the Colonic GHAS score at Week 12, Week 48, and Week 96 (among participants with Colonic histologic disease at baseline per GHAS)

- Statistical Analysis Plan Amendment 1 CNTO1959CRD3004
- Change from baseline in the Subject GHAS Score at Week 12, Week 48, and Week 96 (among participants with histologic disease at baseline per GHAS)
- GHAS-determined Histologic response at Week 12, Week 48, and Week 96 (among participants with histologic disease at baseline per Subject GHAS score)
- GHAS-determined Histologic ileal remission at Week 12, Week 48, and Week 96 (among participants with Ileal histologic disease at baseline per Ileal GHAS score)
- GHAS-determined Histologic colonic remission at Week 12, Week 48, and Week 96 (among participants with colonic histologic disease at baseline per Colonic GHAS score)
- GHAS-determined Histologic remission at Week 12, Week 48, and Week 96 (among participants with histologic disease at baseline per Subject GHAS score)
- GHAS-determined Histo-endoscopic response at Week 12, Week 48, and Week 96
- GHAS-determined Histo-endoscopic remission at Week 12, Week 48, and Week 96
- GHAS-determined Histo-endoscopic remission (Alternative definition) at Week 12, Week 48, and Week 96

Histologic endpoints - Geboes

- Geboes-determined Histologic response at Week 12, Week 48, and Week 96 (among participants with histologic disease at baseline per Subject Geboes score)
- Geboes-determined Histologic ileal remission at Week 12, Week 48, and Week 96 (among participants with Ileal histologic disease at baseline per Ileal Geboes score)
- Geboes-determined Histologic colonic remission at Week 12, Week 48, and Week 96 (among participants with colonic histologic disease at baseline per Colonic Geboes score)
- Geboes-determined Histologic remission at Week 12, Week 48, and Week 96 (among participants with histologic disease at baseline per Subject Geboes score)
- Geboes-determined Histo-endoscopic response at Week 12, Week 48, and Week 96
- Geboes-determined Histo-endoscopic remission at Week 12, Week 48, and Week 96
- Geboes-determined Histo-endoscopic remission (Alternative definition) at Week 12, Week 48, and Week 96

Histologic endpoints – RHI

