The estimates of the treatment difference between the combined guselkumab group or each guselkumab group versus the placebo group will be provided by the difference in the least squares means (LSmeans). The 95% confidence interval (CI) for the differences in LSmeans and p-values will be calculated based on the MMRM. An unstructured covariance matrix for repeated measure within a subject will be used. The F-test will use Kenward-Roger's approximation for degrees of freedom. In case of lack of convergence, empirical structured covariances will be used in the following order until convergence is reached: 1) Toeplitz 2) first order Autoregressive Moving Average. If the normality assumption is in question, an appropriate transformation will be used.

Continuous endpoints involving SES-CD or histologic endpoints that are measured only at Week 12 will be compared using an analysis of covariance (ANCOVA) with treatment as a fixed factor, and baseline score, CDAI (\leq 300 or > 300), baseline SES-CD (\leq 12 or > 12), and Bio-Failure status (yes or no) as covariates. Continuous endpoints involving SES-CD will not include SES-CD strata in the model. Multiple imputation (MI) will be used for imputing missing Total SES-CD data under the assumption that the data are missing at random (MAR). For continuous endpoints involving GHAS and RHI, no imputation will be performed for missing GHAS or RHI values; the missing values will remain as missing. For binary endpoints, NRI will be used to impute missing GHAS, Geboes and RHI endpoints.

After Week 24

Two exploratory endpoints (clinical remission at Week 48, endoscopic response at Week 48) will be controlled for multiplicity. The analyses of the two endpoints will be placed after the 6 sequential tests of the co-primary and secondary endpoints in the multiple testing procedure described in Section 5.4.3.1. If all 6 p-values are <0.05, the testing procedure will continue with the 4 tests of these two endpoints (clinical remission at Week 48, endoscopic response at Week 48, for both dose groups) using the Hochberg procedure (Y Hochberg, Biometrika (1988), 75, 4, pp.800-2) with a 2-sided alpha of 0.05. The Type I error will be controlled over the co-primary, secondary, and these two Week 48 exploratory endpoints in this multiplicity-controlled testing procedure.

The testing of other exploratory endpoints will not be controlled for multiplicity, and nominal p-values will be provided.

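### Geboes ileal remission: the all-items rule can leave disease status missing when grades 2B, 3, 4 and 5 already settle it

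*SAP*

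**What the plan says.** SAP 5.5.1.5 describes the Geboes system as a 7-item scale (grades 0, 1, 2A, 2B, 3, 4 and 5 in Table 5). It sets the ileal result by the worst finding: "The Ileal score is equal to the highest grade with a score > 0", with the example that "a score of 3 for Grade 5 will be a 5.3 regardless of the scores for the other grades". The same bullet then adds the completeness condition: "All items within the ileum must be non-missing to obtain an Ileal score".

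The definitions table that follows works item by item. At the ileal level, active disease means that any of grades 2B, 3, 4 or 5 is not 0. Remission means at or below 2B.0, spelled out as no neutrophils in lamina propria or epithelium, no crypt destruction, and no erosion, ulceration or granulation tissue. Grades 0, 1 and 2A appear in neither definition.

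SAP 5.5.2.10 lists Geboes ileal remission at Weeks 12, 48 and 96, "among participants with Ileal histologic disease at baseline per Ileal Geboes score". SAP 5.5.3 handles missing binary results: "For binary endpoints, NRI will be used to impute missing GHAS, Geboes and RHI endpoints". It carries similar methods forward after Week 24.

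For GHAS, SAP 5.5.1.5 also makes the ileal total missing when an item is missing, but it adds an exception: "if items 1, 4, 5, and 6 are non-missing, then histologic ileal remission (defined in the Table below) can still be determined". Geboes has no such sentence.

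**The concern.** The completeness condition covers seven items, while the status it feeds uses four. If the missing Ileal score is carried through to status, two kinds of participant are misplaced:

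- **Follow-up.** An ileum with 2B, 3, 4 and 5 all scored 0, and only grade 0, 1 or 2A unscored, meets the remission definition. With no Ileal score, the endpoint is missing and is imputed as a failure.
- **Baseline.** An ileum with any of grades 2B to 5 above 0 and some other item unscored certainly has active disease. With no Ileal score, it may not qualify for a denominator defined by that score.

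The first changes a response rate. The second removes eligible participants from the analysis. In both, the data needed to classify the participant are in the database.

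**Working it through.** The plan gives no figure on this point, so there is none to reproduce. The check is logical: does status depend on the item that is missing?

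1. **Inputs.** Table 5 of the SAP gives four levels to each of grades 0, 1, 2A, 2B, 3 and 4 (scores 0 to 3) and five levels to Grade 5 (5.0 to 5.4). Possible complete patterns: 4^6 × 5 = 20,480. Remission requires 2B = 3 = 4 = 5 = 0, which leaves 4^3 = 64 patterns.

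2. **Delete one item at a time** and ask whether the remaining six fix the status. These are counts of patterns, not probabilities.

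| Item unscored | Observed patterns | Remission certain | Active disease certain | Undetermined |
|---|---|---|---|---|
| 0, 1 or 2A (each) | 20,480/4 = 5120 | 4^2 = 16 | 5120 − 16 = 5104 | 0 |
| 2B, 3 or 4 (each) | 5120 | 0 | 5120 − 64 = 5056 | 64 |
| 5 | 20,480/5 = 4096 | 0 | 4096 − 64 = 4032 | 64 |

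   With grade 0, 1 or 2A unscored, status is always settled. With one of 2B to 5 unscored, it is open only when the other three are all 0. Under the all-items rule, none of these patterns has an Ileal score.

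3. **The numeric score is different.** If Grade 5 is unscored, the exact score is fixed in none of the 4096 patterns, because an unread ulcer could always raise it. Requiring completeness for the score itself therefore makes sense. It is too strict only for status.

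4. **Size, under assumptions only.** The documents give no item-missing rate.
   - If each item were unscored independently in a fraction q of ileal reads, the share of true remitters recovered by using only the four relevant grades is (1 − q)^4 × [1 − (1 − q)^3]. That is 0.961 × 0.0297 = 2.9% at q = 1%, 0.922 × 0.0588 = 5.4% at q = 2%, and 0.815 × 0.1426 = 11.6% at q = 5%.
   - Suppose true ileal remission were 35% on guselkumab and 15% on placebo (assumed), and a share m of remitters in both arms were lost. The difference is 20.0 × (1 − m) points: 19.6 at m = 2%, 19.0 at 5% and 18.0 at 10%.
   - If the loss differs by arm, the direction is open. With m = 10% on guselkumab only, the difference is 31.5 − 15.0 = 16.5 points. With m = 10% on placebo only, it is 35.0 − 13.5 = 21.5 points.

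**The case against.** The strongest reply is that the definitions table already solves the problem. Active disease and remission are written as conditions on individual grades, so a programmer could derive both without the Ileal score, and the phrase about the score in SAP 5.5.2.10 could simply name the instrument. This reading is available. It is not the only one, because the GHAS text states an exception for the same situation and the Geboes text does not. A reader comparing the two may conclude that missing is the default for Geboes.

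The GHAS comparison also has a limit. Its exception covers ileal remission, not baseline active disease, and the GHAS endpoints use parallel denominator wording. It therefore supports the follow-up case, while the baseline case rests on the literal text alone.

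Independent loss of single items is also doubtful. All items are read on the same tissue, with the highest value taken over up to two biopsies, and the only missingness the Geboes text describes apart from this rule is loss of a whole region. The true frequency may be very low.

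Three stronger readings are tempting, and the documents do not support them:

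- A reader might infer that Subject-level remission can be declared with Grade 5 unread, because "The Subject score is equal to the highest grade with a score > 0 across the ileum" and the other regions, with no item rule. The remission definition requires GS 5.0, and an unscored grade is not 5.0.
- A reader might infer that GHAS and Geboes would give opposite ileal results only because of this rule. GHAS remission uses epithelial damage and Geboes uses crypt destruction, so the two can differ on histology alone.
- A reader might infer that the treatment effect is biased downward. Remitters can only be lost, but the effect on the difference depends on how missingness falls between arms, which is unknown.

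**Conclusion.** The point stands in a narrow form. Read literally, the SAP can count a participant who meets the Geboes ileal remission definition as a failure, and can exclude a participant with certain ileal disease at baseline. The follow-up case requires that the unscored items are confined to grades 0, 1 and 2A; if one of 2B to 5 is unscored and the others are 0, remission is truly unknown and missing is correct.

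Only Geboes ileal remission at Weeks 12, 48 and 96 is affected. SAP 5.5 treats it as exploratory, with nominal p-values. The co-primary, secondary and multiplicity-controlled Week 48 endpoints do not use it. The percentages above show how the effect scales with an assumed missing rate; they are not estimates for this trial. This is a minor correction, worth making because the wording leaves a classification rule to the programmer.

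**What to change.** Keep the completeness rule for the numeric Ileal score. In the Geboes part of SAP 5.5.1.5, add for ileal status:

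- (i) active disease is present if any available grade among 2B, 3, 4 and 5 is above 0, whatever else is unscored;
- (ii) remission is determined when 2B, 3, 4 and 5 are all scored, and is met only if all four are 0;
- (iii) otherwise status is missing. Unscored grades 0, 1 or 2A never make status missing.

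State in SAP 5.5.2.10 that the ileal denominator uses status (i).

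The cost is a few sentences of SAP text and some derivation code, with no new data. The change should stay at the ileal level. Extending it to Colonic and Subject status would need a separate rule for unscored regions, since protocol 8.1 accepts an endoscopy as complete when the terminal ileum cannot be seen.

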5.5.1.5. Histologic assessment

Histologic assessment will be performed using biopsy samples collected during endoscopy. Two biopsy samples from each of the 5 segments will be collected at screening, Week 12, Week 48, and Week 96 from each of 5 predefined anatomic locations: ileum, right colon, transverse colon, left colon, and rectum.

Biopsies will be collected from representative areas that are consistent with the mucosal appearance visually observed during endoscopy. In a segment with ulcers, all biopsies will be taken from the edge of the ulcer. In a segment without ulcers but with macroscopically abnormal areas, biopsies will be taken from the most inflamed area. In a segment that is endoscopically normal, random biopsies will be taken.

Histologic assessment will be conducted by a group of central expert pathologist readers who are blinded to treatment groups, sites and visits. The modified Global Histology Activity Score (GHAS), Geboes grading scale and Robarts Histologic Index (RHI) will be used to evaluate histologic improvement.

Modified Global Histology Activity Score

The Global Histology Activity Score was first described in 1998, and has been subsequently utilized in a number of studies resulting in peer-reviewed publications (D'Haens et al 1998; D'Haens et al 1999; Mojtahed et al 2014; Baert et al 1999; Laharie et al 2011; Mantzaris et al 2009).

All biopsies for each region will be scored in a blinded manner using the GHAS, with minor adaptations for the circumstances of this study:

- At each time point, all biopsies (up to 2 biopsies per region) obtained from each of the predefined anatomic regions will be scored separately for each of the 8 histological features; feature 8 has been modified from the original GHAS:
 - 1. epithelial damage (scored 0-2)
 - 2. architectural changes (scored 0-2)
 - 3. infiltration of mononuclear cells into the lamina propria (scored 0-2)
 - 4. polymorphonuclear cells in the lamina propria (scored 0-2)
 - 5. polymorphonuclear cells in the epithelium (scored 0-3)
 - 6. the presence of erosions/ulcers (1 for presence and 0 for absence)
 - 7. presence of granulomas (1 for presence and 0 for absence)

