- At each time point, all biopsies (up to 2 biopsies per region) obtained from each of the predefined anatomic regions will be scored separately for each of the 4 items:
- The single highest scoring item from each of the biopsies will be used as the score for that item.
- The weighted sum of the 4 scores within a region will be used as the Total score for that region (range 0-33). Furthermore,
 - The Ileal score will be equal to the Total Ileum Score
 - The worst scores for each item across the right colon, transverse colon, left colon, and rectum will be summed to obtain a Total Colonic Score.
 - The worst scores for each item across the 5 regions will be summed to obtain a Subject Score.

If both biopsies within a region are missing or unevaluable, the RHI will be missing for that region.

The definitions of baseline disease activity and histologic remission using RHI apply to a segment (region), Ileum, Colon, and Subject level. Histologic response, histo-endoscopic response, and histo-endoscopic remission will be evaluated on a subject level only.

Term	Scope	Definition			
Active Disease (RHI)	Subject-level	RHI with a score > 0 for any of Items 2-4 of RHI (lamina propria			
	Ileal	neutrophils, neutrophils in epithelium, or erosions or ulcerations)			
	Colonic				
Histologic Response (RHI)	Subject-level	\geq 50% reduction in RHI score from baseline or sub-scores of lamina propria neutrophils and neutrophils must be equal to 0, with no ulcers or erosions			
Histologic Remission	Subject-level	sub-scores of lamina propria neutrophils, neutrophils in the			
(RHI)	Ileal	epithelium and erosions or ulcerations must be equal to 0.			
	Colonic				
Histo-Endoscopic Response (RHI)	Subject-level	Histologic response and endoscopic response (≥50% improvement from baseline in SES-CD score)			
Histo-Endoscopic Remission (RHI)	Subject-level	Histologic remission and endoscopic remission (SES-CD ≤4 and at least a 2-point reduction from baseline and no subscore greater than 1 in any individual component)			
Histo-Endoscopic	Subject-level	Histologic remission and endoscopic remission (SES-CD Score			
Remission (RHI		≤2).			
Alternative Definition)					

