5.5.3. Analysis Methods

Through Week 24

Exploratory endpoints through Week 24 (eg, clinical remission, clinical response) will be tested regardless of the significance of the co-primary and secondary endpoints; the testing of these exploratory endpoints through Week 24 will not be controlled for multiplicity. Nominal p-values will be presented.

Descriptive statistics (i.e., N, mean, median, SD, IQ range, minimum, and maximum) will be used to summarize continuous variables. Counts and percentages will be used to summarize categorical variables. Graphical data displays (e.g., line plots) may also be used to summarize the data.

The estimand approach and analysis methods specified in Sections 5.4.2.1 and Section 5.4.3.1 for the secondary endpoints will apply to binary endpoints. The ICEs are the same as those specified in Sections 5.4.2.1

For continuous endpoints, the attributes of the estimands will be the same as those specified for the secondary endpoints relative to **Study Intervention**, **Population**, and **ICEs**. If a participant has an ICE in categories 1-3, 5, or 6, baseline values will be assigned from the point of ICE onward. For participants experiencing ICE 4, the associated ICE event will be ignored and any data observed after the associated ICE event will be used for the analysis.

Continuous efficacy endpoints that are collected at multiple post baseline time points through a given visit will be compared using a Mixed Model Repeated Measures (MMRM). The model will include all available data from all treatment groups through that visit for assessing efficacy.

The MMRM model will be used to test the difference between the combined guselkumab group or each guselkumab group versus the placebo group. This model relies on the MAR assumption for the missing responses. Under the assumption of MAR, the missing data will be accounted for through correlation of repeated measures in the model.

The explanatory variables of the MMRM model will include treatment group, visit, applicable baseline score, BIO-Failure status (yes, no), baseline CDAI (\leq 300 or > 300), baseline SES-CD (\leq 12 or > 12), an interaction term of visit with treatment group, and an interaction term of visit with applicable baseline score. Change from baseline in CDAI endpoints will not include CDAI strata in the model, as the baseline CDAI is already included as a factor.

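### Geboes histologic response needs no change from baseline, so anyone entering its denominator with a Subject score of 2B.1 to 3.1 already meets it before treatment

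*SAP*

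**What the plan says.** SAP 5.5.1.5 (Geboes Grading System) takes the Subject score as the highest non-zero grade over the five ileocolonic regions. It then defines three terms on that score:

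- Active disease: above 2B.0, that is, any of grades 2B, 3, 4 or 5 non-zero.
- Histologic response: 3.1 or lower, "indicating neutrophil infiltration in <5% of crypts, no crypt destruction and no erosions, ulcerations or granulation tissue".
- Histologic remission: 2B.0 or lower.

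The response endpoint is listed in SAP 5.5.2.10 as "Geboes-determined Histologic response at Week 12, Week 48, and Week 96 (among participants with histologic disease at baseline per Subject Geboes score". I read histologic disease at baseline as the active-disease definition above.

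The two parallel indices are built differently. GHAS response requires at least a 50% "reduction in subject-level GHAS score from baseline", or absence of the activity features. RHI response requires at least a 50% "reduction in RHI score from baseline or sub-scores of lamina propria neutrophils" and the related features being zero.

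For the analysis, SAP 5.5.3 says that the estimand approach and methods "for the secondary endpoints will apply to binary endpoints". Intercurrent events in categories 1, 2, 3, 5 and 6 therefore make a participant a non-responder. On missing data it adds: "For binary endpoints, NRI will be used to impute missing GHAS, Geboes and RHI endpoints".

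**The concern.** The denominator appears meant to select participants who have something to improve, but it uses the remission threshold (2B.0) while the response threshold is 3.1. Anyone between the two enters the analysis as a responder at baseline. For them the rule scores no change, or worsening up to 3.1, as response.

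This departs from what the SAP usually does with absolute cut-offs. Abdominal pain of 1 or below is assessed among those above 1, and stool frequency of 3 or below among those above 3 (5.5.2.4). CRP of 5 mg/L or below is assessed among those above 5, and fecal calprotectin of 250 µg/g or below among those above 250 (5.5.2.7). Geboes remission follows the same pattern.

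At stake is how the reported Geboes response rates at Weeks 12, 48 and 96 are read. They can be too high in every arm, and the difference between arms may be diluted. A reader could not tell how many responders met the definition before the first dose.

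**Working it through.** **Step 1: list the scores.** Table 5 of the SAP gives these Subject scores above 2B.0:

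- Grade 2B: 2B.1, 2B.2, 2B.3 (3 scores)
- Grade 3: 3.1, 3.2, 3.3 (3 scores)
- Grade 4: 4.1, 4.2, 4.3 (3 scores)
- Grade 5: 5.1, 5.2, 5.3, 5.4 (4 scores)

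The total is 3 + 3 + 3 + 4 = 13. At or below 3.1 there are four: 2B.1, 2B.2, 2B.3 and 3.1. The other nine, 3.2 to 5.4, must fall to count as response. These are scale points, not shares of participants.

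**Step 2: check that the numeric cut-offs match the wording.** The seven items (six with four levels, one with five) give 4^6 × 5 = 20,480 combinations. Forming the Subject score for each and applying both versions of each rule gave no mismatch between the score above 2B.0 and the item-level definition of active disease. It also gave none between the score of 3.1 or lower and the worded definition of response. The overlap is exactly the four scores in Step 1.

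**Step 3: run the same zero-change test on the other indices.** For GHAS and RHI, no combination is active at baseline and also a response with no change. A 50% reduction cannot be met without change, and the alternative route requires the features that define activity to be absent. Geboes remission cannot overlap because its cut-off is the complement of its denominator.

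**Step 4: size, by assumption.** The documents do not give the share f of the denominator with a baseline score of 2B.1 to 3.1. Let p1 and p0 be the response rates among those above 3.1 (guselkumab, placebo). Let q1 and q0 be the share of the 2B.1 to 3.1 group counted as responders after intercurrent events and non-responder imputation. Then:

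- Reported rate in arm i = f·q_i + (1 − f)·p_i
- Reported difference = f·(q1 − q0) + (1 − f)·(p1 − p0)

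Take p1 = 40% and p0 = 20% as assumptions. Each cell shows guselkumab versus placebo in percent, with the difference in points in brackets.

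| f | A: q1 = q0 = 100% | B: q1 = q0 = 80% | C: q1 = 90%, q0 = 70% |
|---|---|---|---|
| 0% | 40 vs 20 (20) | 40 vs 20 (20) | 40 vs 20 (20) |
| 5% | 43 vs 24 (19) | 42 vs 23 (19) | 42.5 vs 22.5 (20) |
| 10% | 46 vs 28 (18) | 44 vs 26 (18) | 45 vs 25 (20) |
| 20% | 52 vs 36 (16) | 48 vs 32 (16) | 50 vs 30 (20) |
| 30% | 58 vs 44 (14) | 52 vs 38 (14) | 55 vs 35 (20) |

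For example, scenario A at f = 20% gives 0.20 × 100 + 0.80 × 40 = 52 and 0.20 × 100 + 0.80 × 20 = 36.

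A rate rises above its value among those above 3.1 when q_i exceeds p_i in that arm. The difference shrinks only when q1 − q0 is smaller than p1 − p0. In scenario C the two gaps are equal, so both rates rise and the difference stays at 20 points.

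**Step 5: test the fix.** With the denominator limited to baseline scores above 3.1, the eligible scores are the nine from 3.2 to 5.4. None of them satisfies response without change.

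**The case against.** The strongest objection is that the affected group may be empty. Entry requires centrally read ulceration in at least one segment. The SAP also directs that "In a segment with ulcers, all biopsies will be taken from the edge of the ulcer", and the Subject score takes the worst grade over five regions. All of this pushes baseline scores towards grade 5. That stands as a reason to expect a small f. It does not settle the matter, because eligibility is endoscopic and no minimum Geboes score is set.

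A second objection is that this is an absolute-state endpoint and reports exactly what it defines. The SAP uses others without a baseline exclusion, such as IBDQ remission. Change in largely the same items is also covered by RHI, which is computed from Geboes grades 1, 2B, 3 and 5. This is fair as to weight. But here the SAP chose to restrict to baseline disease, and the threshold it used does not remove those already in response.

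Third, nothing shows that the treatment comparison is distorted. Scenario C confirms that dilution is not inevitable. At Week 96 a placebo contrast is limited anyway, because unrescued placebo participants stop at unblinding. Both points stand.

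Finally, the table has lost some text in extraction, so a baseline condition could have dropped out of the response row. That is unlikely, since the numeric cut-off and its worded gloss in that row agree. Reading histologic disease more loosely than active disease would only widen the overlap.

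**Conclusion.** The concern holds as a matter of definition: four of the 13 active Subject scores enter the denominator already in response, and a move from 2B.1 to 3.1 counts as success. That conclusion rests only on the SAP's definitions, with histologic disease at baseline read as active disease.

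The practical size is unknown. It depends on f, which the documents do not give and which may be near zero. In the illustration, f between 5% and 30% raises the reported rates by 2.5 to 24 points, depending on arm and scenario (smallest: 20% to 22.5%; largest: 20% to 44%). The difference falls by 0 to 6 points. The endpoint is exploratory with nominal p-values. The co-primary, secondary and multiplicity-controlled Week 48 tests are unaffected. This is a minor point, worth correcting because it is cheap.

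**What to change.** In SAP 5.5.2.10, restrict the Geboes histologic response endpoint to participants with a baseline Subject Geboes score above 3.1. If results already exist under the current rule, keep them and show this as a supplementary analysis beside them. Report by arm the number with a baseline Subject score of 2B.1, 2B.2, 2B.3 or 3.1, which also shows whether the issue matters in practice.

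Leave the Geboes remission denominator (above 2B.0) as it is, so that participants at 2B.1 to 3.1 are still assessed there. Geboes histo-endoscopic response can also stay: it shares the histologic component but needs at least 50% SES-CD improvement, so it cannot be met at baseline.

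The cost is one line of wording and one baseline count, with no new data. The response denominator becomes smaller and differs from the remission denominator. Remission is then no longer nested in response: someone going from 3.1 to 2B.0 counts for remission but lies outside the response analysis. A footnote to the table should say so.
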